#### **Secondary Endpoints**

Secondary endpoints will be summarized at the specified time points using the descriptive statistics described above, individually or in comparison between the treatment groups. Statistical analyses of the following secondary endpoints will be summarized for descriptive purposes and without adjustments for multiplicity:

- Changes in ABI from baseline to hospital discharge, 30 days, 6 months and 12 months post-procedure will be analyzed using paired two-sided Student *t*-tests.
- Changes in Walking Impairment Questionnaire scores from baseline to 30 days, 6 month, and 12 months post-procedure will be analyzed using paired two-sided Student *t*-tests.
- Freedom from Target Lesion Revascularization Kaplan-Meier estimates and plots will be presented to 12 months post-procedure

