	• First occurrence of the following during follow-up: cardiovascular death, or MI, or ischemic stroke, or any amputation above the ankle.
	• Severe bleeding defined according to the Global Utilization of Streptokinase and Tissue plasminogen activator for Occluded coronary arteries (GUSTO) classification
Tertiary Endpoints	• Moderate bleeding defined according to the Global Utilization of Streptokinase and Tissue plasminogen activator for Occluded coronary arteries (GUSTO) classification
Randomization	
 
Patients scheduled for a planned discharge will be randomized on a 1:1 basis using a computerized central randomization portal available through RedCap® to either of the following treatment groups:         
 
ASA (81 mg U.S. sites; 75-100 mg international sites) + clopidogrel: for clinically indicated duration (control arm)
 
ASA (81 mg U.S. sites; 75-100 mg international sites) + Clopidogrel 75mg: for clinically indicated duration +12m (treatment arm)
 
 
 
Randomization will be performed at the within 2 weeks of an eligible procedure
 

Follow-up schedule	All potential subjects will be evaluated for enrollment after the index procedure pre-discharge or within 14 days of the procedure. Follow- up schedule will include patient visits at 30 days and q6 months till the end of study treatment The trial will be considered complete with regard to the primary endpoint after all enrolled subjects have

	completed a 12-month or end of study treatment follow-up evaluation, have died, have a documented premature discontinuation, or whose follow-up window has closed. Follow-up window is $\pm 7$ days for the 30-day visit and $\pm 15$ days for all other visits.

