## **19. Statistical analysis**

Continuous variables will be summarized as mean±standard deviation and compared using the t-test or the Wilcoxon rank-sum test, as appropriate. Discrete variables will be presented as frequencies and group percentages and compared using the chi-square test. For all comparisons a two-sided probability of <0.05 will be considered statistically significant. All analyses were performed using the SAS 9.4 or recent version (SAS Institute Inc., Cary, North Carolina). Primary endpoint will be assessed as per an intention-to treat principle.

Subsequent analysis will also be performed based on per-protocol basis. Pre-specified

subgroup analyses will include:

- 1. Stent vs. non-stent groups
- 2. DES vs. BMS
- 3. Above and below-the knee intervention

4. Claudication vs. CLI groups

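### The only test named for change in ABI and WIQ is a paired t-test against baseline, which does not estimate the randomised contrast; the ABI hospital-discharge time point has no scheduled measurement

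*Combined protocol and SAP*

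**What the plan says.** Section 20, Secondary Endpoints, gives the specific rules for the two measures.

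- ABI: "Changes in ABI from baseline to hospital discharge, 30 days, 6 months and 12 months post-procedure will be analyzed using paired" two-sided Student t-tests.
- WIQ: "Changes in Walking Impairment Questionnaire scores from baseline to 30 days, 6 month, and 12 months post-procedure will be analyzed using paired two-sided Student" t-tests.

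The lead-in to that section allows secondary endpoints to be summarised "individually or in comparison between the treatment groups". It adds that the listed analyses "will be summarized for descriptive purposes and without adjustments for multiplicity".

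Section 19 has a general rule that continuous variables are "compared using the t-test or the Wilcoxon rank-sum test, as appropriate". It also says: "For all comparisons a two-sided probability of <0.05 will be considered statistically significant".

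On timing, Table 2 (Section 12) schedules ABI and WIQ at enrolment, 30 days, 6 months, and 12 months then six-monthly to the end of study treatment. There is no discharge column. The synopsis places enrolment after the procedure: "All potential subjects will be evaluated for enrollment after the index procedure pre-discharge or within 14 days of the procedure".

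**The concern.** The trial randomises 1:1 between two durations of dual antiplatelet therapy. An analysis of ABI or WIQ bears on that question only if it contrasts the arms. A paired t-test asks whether subjects differ from their own baseline, so it mixes the post-procedure course common to both arms with any effect of duration and cannot separate them.

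ABI and WIQ are measures of limb haemodynamics and walking function that the trial already schedules repeatedly. If only paired p-values are reported, that information is not used for the randomised comparison. If the p-values are reported by arm, readers may compare them informally.

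The discharge time point is a separate inconsistency: the analysis text calls for a value that the schedule does not provide.

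**Working it through.** **1. What the documents give.** They state no SD, effect size, baseline correlation or sample size for ABI or WIQ, so there is no planned figure to reproduce. The total of 404 is for the primary endpoint and does not bear on this point. The illustration below borrows 184 evaluable subjects per arm from Section 20, Primary Endpoint (368/2 = 184).

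**2. What each piece of text estimates.**

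| Text | Estimates an arm difference? | Adjusts for baseline? |
|---|---|---|
| Section 20, paired t-test for ABI and WIQ | No | No arm contrast to adjust |
| Section 20 lead-in, between-group summary | Possibly; optional, descriptive, no model named | No |
| Section 19, t-test or Wilcoxon rank-sum | Yes, if applied to these measures | No |

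No ANCOVA or mixed model for these measures appears anywhere.

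**3. Illustration of why paired tests do not inform the contrast.** Suppose both arms have the same true mean change, c, in units of the SD of change. The documents do not give c, so a range is assumed. With n = 184 per arm, the noncentrality is c × √184. Let p be the resulting two-sided 5% power of one arm's paired test. The probability that exactly one arm is significant is 2p(1 − p). The pooled column uses n = 368.

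| Assumed c | p, one arm | Exactly one arm significant | Pooled paired test significant |
|---|---|---|---|
| 0.05 | 0.10 | 19% | 16% |
| 0.10 | 0.27 | 40% | 48% |
| 0.15 | 0.53 | 50% | 82% |
| 0.20 | 0.77 | 35% | 97% |
| 0.30 | 0.98 | 4% | 100% |
| 0.50 | 1.00 | 0% | 100% |

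The true arm difference is zero in every row. A simulation of 20,000 trials at a common change of 0.20 (baseline correlation 0.5) gave 36% discordance between arms, while a between-arm ANCOVA on the same data rejected 4.9% of the time.

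**4. What a baseline-adjusted comparison could detect.** At 80% power and two-sided 5%, the detectable difference in outcome SD units is (1.960 + 0.842) × √(2/184) × √(1 − r²) = 0.292 × √(1 − r²), where r is the baseline/follow-up correlation. For assumed r = 0.3, 0.5 and 0.7 this is 0.28, 0.25 and 0.21. Missing ABI would raise these values.

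**5. Visits where a contrast can appear.** Section 9 sets a 30-day minimum in the control arm, and the test arm takes the indicated duration plus 12 months. At day 30 both arms are therefore assigned the same treatment, apart from the ±7-day visit window. The informative visits are 6 and 12 months, and less so for subjects whose indicated duration runs past them.

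**6. Timing of the discharge ABI.** Section 20 lists four post-baseline ABI times: discharge, 30 days, 6 months and 12 months. Table 2 schedules three of the four; discharge is the exception. The only baseline visit is enrolment. For a subject enrolled after discharge, the baseline-to-discharge interval runs backwards. For a subject enrolled before discharge it is short, and no second ABI is scheduled. Section 24 (Risk minimization) mentions pre-procedure history, examination and laboratory work, but not ABI.

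**The case against.** The strongest reply is that the plan does allow a between-arm comparison. The Section 20 lead-in mentions one, and the Section 19 rule could be applied to ABI and WIQ. The analyses are also declared descriptive, and Section 6 lists neither measure as a secondary or tertiary endpoint, so no listed conclusion rests on them. This stands as a limit on severity. It does not close the gap: the lead-in leaves the comparison optional, the Section 19 rule is unadjusted and generic, and the rule written specifically for these measures is the paired test. Section 19 also attaches a 0.05 significance threshold to all comparisons, so a descriptive label does not prevent significance claims.

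Several stronger readings are tempting, but the documents do not support them.

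- A reader might infer that the tests are to be run within each arm and the arms' p-values compared. The text says neither. The table above shows what would follow if someone did so.
- A reader might infer that change to discharge cannot be computed. It is unscheduled, but some subjects are enrolled before discharge, so it is not impossible for everyone.
- A reader might infer that ABI and WIQ are the only limb measures taken at every visit. Table 2 also records Rutherford class at each one, and the Appendix gives WIQ only at baseline and six-monthly.
- A reader might measure the loss by the variance of ANCOVA relative to a between-arm change-score test, (1 + r)/2. Section 20 names no such test, so that ratio is not the cost of the planned analysis.

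**Conclusion.** The point holds and is minor. The plan names a within-subject test for change in ABI and WIQ and specifies no baseline-adjusted comparison of the randomised arms. This follows from the text and needs no assumption. The primary endpoint and the endpoints listed in Section 6 are unaffected.

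The discordance figures (0% to 50%) and the detectable differences (0.21 to 0.28 SD) are illustrations. They rest on assumed changes and correlations and on 184 subjects per arm with complete data.

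The mismatch between the discharge ABI and Table 2 is also real. It is a matter of reconciling the text and defining baseline.

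**What to change.** 1. In Section 20, make the analysis of ABI and WIQ a between-arm ANCOVA at each visit, or a mixed model with arm-by-visit terms, with the enrolment value as covariate. Report the adjusted difference and 95% CI at 30 days, 6 months and 12 months, treating 6 and 12 months as the informative visits. Do not report one effect averaged over visits, because day 30 would dilute it. Paired changes may stay as descriptive summaries by arm.
2. State that baseline means the enrolment value. Then remove hospital discharge from the ABI time points, or say which two measurements are meant and add them to Table 2.
3. While editing, align the WIQ times: Table 2 and Section 20 include 30 days; the Appendix does not.

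The cost is SAP wording; removing the discharge point needs no new visits or subjects. The small downside is incomplete ABI: Table 2, footnote 4, allows phone visits, with ABI taken from medical records only where available. The amount missing by arm should be reported. The mixed model uses subjects with some visits missing, but relies on the missing values being explained by the observed data.

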## 5. Trial hypothesis

We hypothesize that DAPT with ASA and clopidogrel administered for an additional 12 months after a clinically indicated duration following iliac, FP or BTK endovascular intervention will improve primary patency, limb salvage, freedom form ischemic stroke and survival, in patients with symptomatic PAD.

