## 6. Trial endpoints

Clinical endpoints will be analyzed in all subjects who are enrolled, regardless of whether the trial treatment administered successfully completed for the desired duration. A subject will be considered enrolled in the trial when he/she is randomized to one of the treatment arms of the study. All endpoints are subject-based unless otherwise specified.

The primary endpoint is subject-based of the longer of a 12-month or end of study treatment endpoint of the first occurrence of index limb arterial occlusion, surgical intervention,

endovascular intervention, amputation of the affected limb (primary patency and limb salvage), MI, ischemic stroke or death (survival)

The secondary endpoints are subject-based on the longer of a 12-month or end of study treatment endpoints that include: (a) the first occurrence of any individual component of the primary endpoint, (b) the first occurrence of the following during follow-up: cardiovascular death, or MI, or ischemic stroke, or any amputation above the ankle and (c) severe bleeding defined according to the Global Utilization of Streptokinase and Tissue plasminogen activator for Occluded coronary arteries (GUSTO) classification

The tertiary endpoint is based on the longer of a12-month or end of study treatment moderate bleeding according to the GUSTO classification

Clinically indicated DAPT duration will be based on the longest pre-discharge following index peripheral intervention procedure DAPT duration. This will be determined based on: peripheral intervention device IFUs, preceding coronary intervention, acute coronary syndrome or other guideline-based clinical or device specific DAPT duration.

Study treatment will be discontinued at the first occurrence of a primary endpoint as defined in the table below. Patients, however, can resume taking aspirin, Clopidogrel, or both based on their provider's clinical decision.

Primary endpoint definition(s)	Secondary/Tertiary endpoint definition(s)
Occlusion of the target limb documented by any imaging procedure performed clinically	As described in section 6, except for:
any maging procedure performed ennearly	GUSTO bleeding criteria:
Any surgical or endovascular	1. Severe or Life-threatening: Intracerebral hemorrhage resulting in substantial
revascularization procedure on the index limb	hemodynamic compromise requiring treatment
Amputation above the ankle of the index	2. Moderate: Requiring blood transfusion but not resulting in hemodynamic

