## 16. Eligibility of subjects, exclusions and missing data

All subjects who are enrolled will be eligible for evaluation, regardless if they receive the control or active arm drug treatments for the assigned durations or not. Sensitivity analyses to account for missing data will be performed and may include imputation of missing data if deemed appropriate. The distribution of prognostic factors between subjects with and without data will be examined. Statistical models that account for censored data will be employed in appropriate circumstances, e.g., for time-to-event outcomes. Outlier values will be evaluated for their validity. All data will be included unless judged to be invalid. The robustness of the primary endpoint conclusion will be assessed based on these analyses.

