## **Primary Endpoint**

For the primary endpoint of 12-month composite of primary patency, limb salvage, MI, ischemic stroke and survival, with 95% confidence bounds will be calculated in the active arm and compared to control treatment duration. If this bound is less than that of control, then the primary endpoint will be considered met. All enrolled subjects are to be assessed for adverse events at follow-up visits. Assuming a maximum of 10% attrition due to non-compliance, loss to follow-up or death or non-compliance with follow-up, a minimum of 184 subjects in each arm are expected to be evaluable for the primary endpoint.

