#### **Other Analysis Methods**

Kaplan-Meier plots of time-to-event variables will be constructed for clinical outcomes.

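### Kaplan-Meier for target lesion revascularisation, with no rule for death as a competing event, would slightly overstate the proportion of patients revascularised

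*Combined protocol and SAP*

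**What the plan says.** Section 20 (Secondary Endpoints) lists, as one of three items, freedom from TLR, for which "Kaplan-Meier estimates and plots will be presented to 12 months post-procedure". These items "will be summarized for descriptive purposes and without adjustments for multiplicity". Section 20 (Other Analysis Methods) adds one general sentence: "Kaplan-Meier plots of time-to-event variables will be constructed for clinical outcomes". It does not name the outcomes or give a time horizon.

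Section 6 makes a secondary endpoint of "the first occurrence of any individual component of the primary endpoint", and also of a composite that counts cardiovascular death only. Both are followed to the longer of 12 months or the end of study treatment.

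On censoring, Section 16 says only that "Statistical models that account for censored data will be employed in appropriate circumstances, e.g., for time-to-event outcomes". Section 20 (Primary Endpoint) counts death among the reasons for attrition: "Assuming a maximum of 10% attrition due to non-compliance, loss to follow-up or death". No section says how a death before a non-fatal event is handled, and cumulative incidence is not mentioned. All-cause death is itself a component of the primary endpoint (Section 6 table).

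**The concern.** A patient who has died can no longer have a TLR. If the death is censored, Kaplan-Meier treats that patient as if the later risk were the same as that of patients still alive. One minus Kaplan-Meier then estimates the risk in a hypothetical setting without deaths, not the share of randomised patients who have a TLR. It is too high whenever deaths occur.

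Deaths are to be expected. Section 1 cites mortality of up to 30% at 5 years in this disease. Section 5 hypothesises that longer treatment "will improve primary patency, limb salvage, freedom form ischemic stroke and survival", so mortality could differ between the arms, and the excess would then differ too.

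At stake is the accuracy of a descriptive result: the TLR curve, and any Kaplan-Meier plot drawn for another non-fatal outcome.

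**Working it through.** **The plan's own figures.** The plan gives no expected TLR rate and no allowance for competing deaths, so there is no figure on this point to reproduce. Its sample size can be checked for context. For 49% against 34%, two-sided 0.05 and 80% power, the continuity-corrected two-proportion formula gives 182 per arm, or 364 in total. Then 364/0.90 = 404.4, against 404 stated. That calculation concerns the primary composite, which includes death, so nothing below changes it.

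**Inputs**

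- Mortality: up to 30% at 5 years (Section 1). At a constant hazard the yearly risk is 1 − 0.70^(1/5) = 6.9%, and the hazard is m = −ln(0.70)/5 = 0.0713.
- 12-month TLR: 25% with clopidogrel and 32.4% with placebo, from the earlier randomised trial described in Section 3. These are counts with percentages; I treat them as Kaplan-Meier risks, which is an assumption.
- 202 patients per arm (Section 14).

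**Formulas**, assuming constant hazards, with l the TLR hazard and m the death hazard per year:

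- One minus Kaplan-Meier with deaths censored: 1 − exp(−l), so l = −ln(1 − Kaplan-Meier risk).
- Cumulative incidence: l/(l + m) × [1 − exp(−(l + m))].

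**At 6.9% yearly mortality**

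- Risk 25%: l = 0.2877. Cumulative incidence = 0.2877/0.3590 × (1 − 0.75 × 0.9311) = 24.2%. Excess 0.8 points.
- Risk 32.4%: l = 0.3916. Cumulative incidence = 0.3916/0.4629 × (1 − 0.676 × 0.9311) = 31.3%. Excess 1.1 points.

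**Over a range of assumed one-year mortality** (excess in percentage points)

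| One-year mortality | TLR 25% | TLR 32.4% |
|---|---|---|
| 2% | 0.2 | 0.3 |
| 5% | 0.6 | 0.8 |
| 6.9% | 0.8 | 1.1 |
| 10% | 1.2 | 1.5 |
| 15% | 1.8 | 2.3 |
| 20% | 2.5 | 3.1 |

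The largest value is 32.4 − 29.251 = 3.149.

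**Difference between arms.** Take Kaplan-Meier risks of 25% (longer treatment) and 32.4% (control), a difference of 7.4 points. The unequal mortalities are illustrative.

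| One-year mortality, longer / control | Cumulative incidence | Difference | Change from 7.4 |
|---|---|---|---|
| 6.9% / 6.9% | 24.2% / 31.3% | 7.2 | −0.2 |
| 5% / 7% | 24.4% / 31.3% | 6.9 | −0.5 |
| 5% / 10% | 24.4% / 30.9% | 6.5 | −0.9 |
| 10% / 5% | 23.8% / 31.6% | 7.8 | +0.4 |

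The standard error of such a difference is about √[(0.25 × 0.75 + 0.324 × 0.676)/202] = 4.5 points.

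**Beyond 12 months.** If a curve ran to 24 months at the 32.4% hazard and 6.9% yearly mortality (both continued by assumption), one minus Kaplan-Meier would be 1 − 0.676² = 54.3% and the cumulative incidence 51.1%, an excess of 3.2 points.

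**The case against.** The strongest reply is that little in the plan depends on this.

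- **The documents do not say that deaths are censored.** That is correct. It is inferred from the method named. It is still the ordinary reading, because counting death as an event would no longer estimate freedom from TLR. If another rule is meant, the plan has to state it.
- **The components are not estimated by Kaplan-Meier.** A reader might infer that mortality biases the component results upward and so obscures which part of the composite moved. The documents do not support this. Section 20 summarises secondary endpoints with the descriptive statistics set out in Section 19, which for discrete outcomes are percentages compared by chi-square. A crude percentage does not censor deaths. Kaplan-Meier estimates are specified only for TLR, which is not itself a component: the composite counts any revascularisation of the index limb. The components are touched only if they are among the unnamed outcomes to be plotted.
- **The arm comparison is hardly moved.** A reader might infer from the survival hypothesis that the comparison is distorted. No test of TLR between arms is specified, the analysis is descriptive, and the shift is under 1 point against a standard error of 4.5. Its direction depends on which arm has more deaths. A comparison of cause-specific hazards, which censors deaths, would also remain interpretable.
- **The higher mortality assumptions are pessimistic.** Entry requires an estimated survival of at least 1 year (Section 10), and the documents' only mortality figure implies about 6.9% a year. The rows above that show sensitivity, not expectation.

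All four points limit the size and reach of the problem. None makes one minus Kaplan-Meier the right estimate of the proportion with TLR.

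**Conclusion.** The point holds as a refinement of reporting. With deaths censored, the planned TLR estimate would overstate the proportion revascularised by 12 months by about 0.8 to 1.1 points, roughly 3% in relative terms, on the documents' own mortality and TLR figures. Curves carried past 12 months would show more.

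This rests on constant hazards, on a 5-year mortality figure converted to a yearly rate, on the earlier trial's proportions standing in for Kaplan-Meier risks, and on deaths being censored. The primary composite includes all-cause death, so neither its result nor the sample size is affected. Claims of biased component percentages or a materially distorted treatment comparison go further than the documents allow.

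**What to change.** In Section 20:

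1. Replace the Kaplan-Meier estimate of freedom from TLR with Aalen-Johansen cumulative incidence of TLR by arm, with death as the competing event. Do the same for any Kaplan-Meier plot of a non-fatal outcome under Other Analysis Methods.
2. Show mortality by arm alongside these curves.
3. If the Section 6 composite that counts only cardiovascular death is plotted, treat non-cardiovascular death as the competing event.
4. Keep Kaplan-Meier for the primary composite and for all-cause death.

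The cost is a few lines of text and a standard option in the analysis software. No additional patients, visits or data are needed. Free improvement.
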